5.1 Description

The Orbera (Apollo Endosurgery, Austin Tx) is an elastic spherical balloon made of silicone, filled with 450 to 700 mL of saline solution, and is FDA approved for weight loss in adult US patients with body mass index between 30 to 40 kg/m². The deflated balloon comes preloaded on a catheter, which is blindly advanced transorally into the stomach. An endoscope is then advanced alongside it to ensure accurate placement of the balloon in the fundus. Under direct visualization, the balloon is then inflated by injecting saline solution through the external portion of the catheter. The Orbera balloon is currently used in many countries outside the United States and is typically implanted for 6 months and then retrieved endoscopically.

5.2 Method for Assigning Subjects to Treatment Groups

All enrolled subjects will get the Orbera intragastric balloon and paired EUS guided liver biopsies.

5.3 Preparation and Administration/Implantation of Investigational Device

The intragastric balloon will be used as described by the Orbera PMA application approved by the FDA.


5.5 Prior and Concomitant Therapy

Not applicable

5.6 Packaging and Labeling

Upon receipt of the IGB devices from Apollo Endosurgery, assurance of the investigational device label will be affixed to the packaging of each device. See below:

“CAUTION – Investigational Device. Limited by Federal (or United States) law to investigational use”

5.7 Masking/Blinding of Study

Not applicable

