3.1 General Design

Patients with suspicion for NASH at our center undergo a combined MRE/MRS (magnetic resonance elastography/magnetic resonance spectroscopy) sequence to classify their disease according to four stages. These stages are numbered from 1-4 with stage 4 signifying more advanced fibrosis. The MRE/MRS sequence also quantifies hepatic fat content. Those with stage 1-3 fibrosis will be referred for IGB placement for weight loss as a management strategy for NASH. Once referred to the endoscopic bariatric clinic a multidisciplinary team that includes endocrinology, gastroenterology, psychology, and nutrition will evaluate them. If found to be appropriate candidates, they will be enrolled in this study by a member of the study team who will discuss the study protocol, risks, benefits, and alternatives with patients and have them sign an informed consent. Patient will undergo intragastric balloon placement and an EUS guided liver biopsy during the same endoscopy session will be performed under monitored anesthesia sedation at our outpatient endoscopy unit. The EUS guided liver biopsy will be performed before balloon insertion from the left liver lobe under EUS guidance using a 22 gauge core needle (Sharkcore, Covidien, Minneapolis, MN). Three passes will be performed from two separate liver segments (Figure 2). An additional pass may be performed at the discretion of the PI if the three performed passes do not yield enough tissue on visual inspection of the core to ensure adequate histology analysis. The maximum number of passes will not exceed four. Doppler ultrasound will be used to exclude intervening vessels. Two samples will be submitted for histopathology review in formalin, and one or two will be submitted for total fat

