Of note in this protocol will include patients with diagnosis of NASH with fibrosis (stage 1-3) on MRE/MRS (magnetic resonance elastography/magnetic resonance spectroscopy), which has demonstrated high accuracy in making the diagnosis, but has unknown sensitivity and specificity to detect change over time and has no standardized validated criteria to objectively assess improvement in NASH and fibrosis as exists for liver biopsy, which remains the gold standard in clinic trial evaluating the impact of intervention on NASH. **In the rare instance that the MRE result was falsely positive and the patient was not found to have NASH on liver biopsy. The patient will continue with balloon therapy for weight loss, but we will not repeat liver biopsy at 6 months, since the balloon is indicated for obesity with or without NASH with clear health benefits to weight loss in this cohort.** The balloon cost will remain covered by the study under these rare circumstances.

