3.2 Primary Study Endpoint

Number of subjects with ≥ 2 points improvement in NASH activity scores on paired liver biopsies before and 6 months after intragastric balloon placement.

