6.3 Tissue lipidomics workup

A total of 50 mg of liver tissue will be collected via EUS-guided biopsy. Sharkcore needle is 22 gauge. Diameter is ~0.7 mm. ~270 mm of tissue length will be acquired and will deliver a volume of ~50 mg. The sample will be frozen in liquid nitrogen immediately upon harvesting in the endoscopy suite and placed in a 1.5 conical Eppendorf tube. Samples shall not sit more than few minutes before flash freezing to ensure adequate analysis. Also, inspection before freezing will occur to ensure that the tissue is relatively clean specimen on inspection.

7 Statistical Plan

Baseline subject characteristics will be described by their means, medians and and/or frequencies. For our primary study endpoint of improvement in NASH activity scores on paired liver biopsies at baseline and after 6 months, we will be using a paired t-test with two sided alpha <0.05. With a sample size of 20 subjects, we will have 80% power to detect a medium to large difference in activity scores (0.66). Please see table below for minimum sample size needed for each desired effect size.

	Small effect size 0.5	Medium effect size 0.66	Large effect size 0.8
Sample (N)	34	20	15

Additionally, we will run a linear regression analysis with the change in NASH activity scores as the outcome with baseline BMI and diabetes as the covariates on a univariable and multivariable fashion to investigate their effects on the primary outcome.

For our secondary endpoint of number of subjects with regression of fibrosis in paired liver biopsies, we will be reporting the percentage of subjects with regression. As far as the secondary endpoint of percent total body weight 6 months after Orbera balloon placement, we will be reporting the mean or median percent total body weight loss at 6 months.

For our secondary endpoint of quantifying total fat liver and triglycerides content, we will be reporting the mean and median percent of change at 6 months.

8 Safety and Adverse Events

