8.5 Unblinding Procedures

Not applicable

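### Histology reading is not masked to time point, so a shift in scoring between baseline and month 6 would count as improvement in NAS and fibrosis

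*Combined protocol and SAP*

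**What the plan says.** Section 5.7 ("Masking/Blinding of Study") and section 8.5 ("8.5 Unblinding Procedures") are both answered as not applicable. The Study Summary calls the study open label, and section 5.2 confirms that there is one arm: "All enrolled subjects will get the Orbera intragastric balloon and paired EUS guided liver biopsies".

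On how the tissue is read, section 3.1 says only: "Two samples will be submitted for histopathology review in formalin". Sections 5.4 and 6 repeat this. Sections 3.1, 4.3, 5.4 and 6 add that the study pays for the pathologic interpretation. Nothing states who reads the slides, how many readers there are, whether slides are coded, in what order they are read, or whether the reader knows the time point.

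Section 3.1 also covers the case where "the MRE result was falsely positive and the patient was not found to have NASH on liver biopsy": that patient keeps the balloon but has no second biopsy.

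The primary endpoint in section 3.2 counts subjects with at least two points of "improvement in NASH activity scores on paired liver biopsies before and 6 months after intragastric balloon placement". For the same scores, section 7 states "we will be using a paired t-test with two sided alpha" below 0.05. Fibrosis regression on the paired biopsies is a secondary endpoint in section 3.3.

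**The concern.** Masking of treatment and masking of the outcome reader are separate questions. Section 5.7 settles the first and leaves the second open.

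NAS and fibrosis stage are scores that a pathologist assigns. The endpoints in question are differences between two such scores on the same subject. The rule in section 3.1 means that the baseline slide gets a reading about six months before the month-6 slide exists. If those real-time readings supply the endpoint data, the two scores come from separate sessions, and the second can be known to be post-balloon. The protocol also says openly, in section 1.5.3, that histology is expected to improve.

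Two things can then move the score without any change in the liver: the reader's expectation, and drift in scoring habits over time. With no concurrent control, either looks the same as a treatment effect, and no planned analysis can separate them. At stake are the primary responder count, its paired t-test and the fibrosis-regression percentage. The weight, MRS and lipidomic endpoints are not affected.

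**Working it through.** **1. The plan's own figure.** Section 7 gives N = 20 for 80% power at a standardized effect of 0.66, paired t-test, two-sided 0.05. Noncentrality is 0.66 × √20 = 2.95 with 19 degrees of freedom and critical value 2.093. Power is 79.9%, so the stated figure reproduces. The concern does not depend on it, and masking the reader leaves N unchanged.

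**2. Is masked reading provided anywhere?** Sections 3.1, 5.4 and 6 describe sampling and submission only. Section 7 describes the test only. Sections 5.7 and 8.5 are not applicable. The one use of a word like blind elsewhere (sections 1.2 and 5.1) describes how the catheter is advanced. A later masked re-read is neither planned nor ruled out.

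**3. How much a reading shift would matter.** From the plan: n = 20, paired t-test, two-sided 0.05, responder threshold 2 points. Assumed, because the documents give neither: a mean reading shift of 0.1 to 1.0 NAS points towards improvement, and an SD of the paired change of 1.5, 2.0 or 2.25 points. True change is set to zero.

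Chance of a significant improvement = P(T > 2.093), where T is noncentral t with 19 df and noncentrality (shift / SD) × √20. Example: shift 0.5 and SD 2.0 give 0.25 × 4.472 = 1.118, hence 18.5%.

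Expected responders = 20 × P(Z > (1.5 − shift) / SD). The cut is 1.5 because changes are rounded to whole points. Example: shift 0.5 and SD 2.0 give 20 × P(Z > 0.5) = 20 × 0.3085 = 6.2.

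| Reading shift (points) | Significant improvement, SD 1.5 / 2.0 / 2.25 | Expected responders of 20, same SDs |
|---|---|---|
| 0 | 2.5% / 2.5% / 2.5% | 3.2 / 4.5 / 5.0 |
| 0.1 | 4.7% / 4.0% / 3.8% | 3.5 / 4.8 / 5.3 |
| 0.25 | 10.5% / 7.7% / 6.8% | 4.0 / 5.3 / 5.8 |
| 0.5 | 29% / 18.5% / 15.5% | 5.0 / 6.2 / 6.6 |
| 1.0 | 81% / 56% / 47% | 7.4 / 8.0 / 8.2 |

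Extra false responders over the zero-shift row are 0.7 to 0.9 at 0.25 points, 1.5 to 1.9 at 0.5 and 3.2 to 4.2 at 1.0.

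A check with 100,000 simulated trials of whole-point changes gave 10.5 / 7.7 / 6.7% at 0.25, 28.7 / 18.3 / 15.4% at 0.5 and 79.6 / 55.8 / 46.8% at 1.0.

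For scale, the planned detectable effect of 0.66 SD is 0.66 × 1.5 = 1.0, 0.66 × 2.0 = 1.3 or 0.66 × 2.25 = 1.5 points.

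**4. If there is a true improvement.** Take a true mean change of 1 point, again assumed. Without a shift, expected responders are 20 × P(Z > 0.5 / SD) = 7.4 / 8.0 / 8.2. With a 0.5-point shift they are 20 × P(Z > 0) = 10.0 at every SD. The shift adds 1.8 to 2.6 responders and adds 0.5 points directly to the estimated mean change.

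**The case against.** The strongest reply is that this is silence rather than error. Not applicable is the correct entry for an open-label single-arm study, and slide reading may be governed by a pathology procedure outside the protocol. No section cites one, but the conclusion must stay at what is not stated: the reader can know the time point, not that the reader will.

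Second, the magnitude is wholly assumed. The SDs of 0.75 and 2.25 in sections 1.1 and 1.5.1 describe scores in another study, not paired change. This stands: the table shows sensitivity, not a likely size.

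Third, the plan's own evidence points to real improvement. Section 1.1 reports lower NAS in 32% of patients losing 5% or less and in all who lost 10% or more, and section 1.5.1 expects about 13% loss with the balloon. A false-positive t-test is then not the main risk. That is fair, but step 4 shows that the harm becomes an inflated effect and responder count, which is no less a problem for a study meant to estimate them.

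Fourth, noise alone gives 3.2 to 5.0 responders, more than a 0.5-point shift adds. The lack of a control is indeed the larger limitation. Masked reading does not remove it, nor differences in processing between slides prepared six months apart. It does remove one bias that can be avoided.

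Finally, a pathologist who made the real-time reads might recall some cases. That is a residual weakness, reduced by coding and random order.

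**Conclusion.** The concern holds. As written, the plan lets the pathologist know which biopsy is post-balloon when scoring the primary endpoint and fibrosis regression, and the single-arm design has no means of separating a reading shift from a histological change. The textual finding rests on the supplied protocol alone; an uncited pathology procedure could already provide masking.

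The size is conditional on the assumed shift and SD. A shift near 0.1 points is of little consequence. From about 0.5 points, roughly a third to half of the detectable effect at these SDs, it matters for both the t-test and the responder count. This does not invalidate the endpoint. It is an avoidable weakness that should be corrected, and confidence in its practical importance is medium.

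**What to change.** State the following in sections 5.7 and 7:

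- After the last month-6 biopsy, the study coordinator codes all baseline and month-6 slides so that subject, date and time point are hidden.
- One pathologist, from those already reading for the study, scores them as a single batch in random order, not presented as identified pairs. If more than one pathologist reads, one who did not make the real-time baseline reads is preferable.
- The code key is opened only after all scores are recorded.
- These masked scores alone supply NAS and fibrosis stage for the endpoints in sections 3.2 and 3.3. The real-time baseline read serves only the NASH decision in section 3.1.

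Hiding the time point deals with expectation, and the single batch in random order deals with drift. If this is already the practice, stating it in the two sections is enough.

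The cost is slide coding, one extra reading session and a wait for histology results until the last month-6 biopsy. The session covers about 40 slide sets (20 subjects × 2) and at most 50 (25 × 2). The upper end is unlikely, because the extra five subjects are there to cover early withdrawals and subjects without NASH have no second biopsy. No extra biopsy, visit or subject is needed, and no extra reader if a pathologist already reading for the study does it.

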5.8 Receiving, Storage, Distribution and Return

5.8.1 Receipt of Investigational Devices

The Orbera intragastric balloon devices will be shipped to the study coordinator from Apollo Endosurgery in Austin, Texas. Upon receipt of the devices, the study coordinator will perform an inventory and fill out a device accountability log to ensure that all devices are accounted for. Any discrepancies, damaged, or unusable devices in a given shipment will be documented in the study files and the company will be notified. The devices will then be taken by the study coordinator to where they will be stored in the Operating Room Core.

5.8.2 Storage

The Orbera intragastric balloons will be stored with the rest of the supplies that will be stored in the Operating Room Core which is a secure location with limited access to prevent unintended or unauthorized use of the device.

5.8.3 Distribution of Study Device

The Orbera intragastric balloons will be distributed according to the clinical protocol of how clinical intragastric balloons are distributed. The serial number on the Orbera intragastric balloon will be matched up to a subject's medical record number. This de-identified data will then be recorded on the device accountability log using subject number instead of medical record number.

5.8.4 Return or Destruction of Study Device

At routine intervals and at the completion of the study, there will be a reconciliation of devices shipped, devices utilized, and devices remaining. This reconciliation will be logged on the Device Accountability form, signed and dated. Any discrepancies noted will be documented, the sponsor-investigator will be notified and an investigation will be conducted to determine the cause of the discrepancy. Devices destroyed on site will be documented in the study files.

6 Study Procedures

Patients with suspicion for NASH at our center undergo a combined MRE/MRS (magnetic resonance elastography/magnetic resonance spectroscopy) sequence to classify their disease according to four stages. These stages are numbered from 1-4 with stage 4 signifying more advanced fibrosis. The MRE/MRS sequence also quantifies hepatic fat content. Those with stage 1-3 fibrosis and interested in weight loss with the intragastric

balloon will be referred for the intragastric balloon clinic evaluation, which consist of one day evaluation by nutrition, psychology, and gastroenterology in the obesity clinic. Those who meet the inclusion / exclusion criteria will be consented to participate in the study after discussion of risk, benefits, and alternatives by one of our study team members and a written consent is provided. Following this, patients will be scheduled for their intragastric balloon placement and EUS guided liver biopsy.

Patients will undergo intragastric balloon placement and an EUS guided liver biopsy during the same endoscopy session will be performed under monitored anesthesia sedation at our outpatient endoscopy unit. The EUS guided liver biopsy will be performed before balloon insertion from the left liver lobe under EUS guidance using a 22 gauge core needle (Sharkcore, Covidien, Minneapolis, MN). Three passes will be performed from two separate liver segments (Figure 2). An additional pass may be performed at the discretion of the PI if the three performed passes do not yield enough tissue on visual inspection of the core to ensure adequate histology analysis. The maximum number of passes will not exceed four. Doppler ultrasound will be used to exclude intervening vessels. Two samples will be submitted for histopathology review in formalin, and one or two will be submitted for total fat quantification analysis. After the EUS guided liver biopsy (usually take 10 minutes to perform), the Orbera intragastric balloon will be advanced to the stomach under endoscopy guidance and inflated with 600 ml of normal saline. Patient transient nausea and pain symptoms will be managed with few days course of antiemetic and antispasmodics as per our clinical protocol. Patient will also be required to take a proton pump inhibitor -if not already taking- throughout the 6 months of balloon therapy. Patient will then undergo a moderate intensity life-style intervention consisting of daily phone call for the first week (nurse and or study coordinator) then monthly group visits with a health-care coach / nutrition to administer the life-style intervention program over 6 months period as per our clinical protocol for the intragastric balloon. At 6 months patients will return for balloon removal at our complex endoscopy unit under monitored anesthesia care. The balloon will be removed using the standard balloon retrieval kit approved by the FDA. After balloon removal a second EUS guided liver biopsy from two separate liver segments similar to the first biopsies site will be obtained with three or four passes with the 22 gauge core liver biopsy needle (Sharkcore, Covidien, Minneapolis, MN). The anticipated procedural length for both the EUS guided liver biopsy and balloon insertion and removal is less than 6 minutes. After balloon removal, all patients will be offered additional six months of moderate life-style intervention program administered as monthly group or individual visits with a health care coach to emphasize healthy lifestyle intervention and behaviors. Weight, height, waist circumference, and demographic information will be collected a baseline, time of balloon removal (6 months), and at 12 months (6 months after balloon removal). Of note the cost of balloon placement, removal, medications to manage symptoms after balloon placement, EUS guided liver biopsy and pathologic interpretation, and the 12 months life-style intervention program will be covered by the study. The initial evaluation at the obesity clinic prior to enrollment in the study will be part of regular clinical care. The PI will evaluate all patients within 1 week of balloon placement and removal.

6.1 Follow up for Patients with Device-Related Adverse Events at the Time of Device Removal

Patients with any device related adverse events (AE) or gastric ulcerations at the time of device removal will continue on medical proton pump inhibitors therapy with dose and duration of therapy determined by the study PI. These patients will be followed clinically until complete resolution. Repeat endoscopy to assess for resolution will be done at the discretion of the study PI depending on the severity of endoscopic finding at the time of removal and the clinical need based on best clinical guidelines and practices.

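### A fourth baseline pass is triggered by short histology tissue, but the stated sample split holds histology at two samples and lets only fat quantification grow

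*Combined protocol and SAP*

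**What the plan says.** The biopsy paragraph appears in near-identical form in protocol sections 3.1, 5.4 and 6.

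- **Baseline passes.** Three passes are planned, from two liver segments. The PI may add one "if the three performed passes do not yield enough tissue on visual inspection of the core to ensure adequate histology analysis". A ceiling follows: "The maximum number of passes will not exceed four".
- **Baseline split.** "Two samples will be submitted for histopathology review in formalin, and one or two will be submitted for total fat quantification analysis".
- **Month 6.** The second biopsy "will be obtained with three or four passes with the 22 gauge core liver biopsy needle". No reason is given for choosing four over three, and no split is stated.
- **Lipid tissue (section 6.3).** "A total of 50 mg of liver tissue will be collected via EUS-guided biopsy". The section equates this to roughly 270 mm of core. It requires the sample to be frozen in liquid nitrogen straight after harvest, with a delay of no more than a few minutes.
- **Use of the histology.** The primary endpoint (section 3.2) counts subjects with at least 2 "points improvement in NASH activity scores on paired liver biopsies before and 6 months after intragastric balloon placement". For the change in score, section 7 says "we will be using a paired t-test with two sided alpha <0.05". Fibrosis regression (section 3.3) is read from the same biopsies.

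No section sets a minimum core length or portal-tract count for an adequate histology specimen. None says which core goes to which analysis.

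**The concern.** The reason for the extra pass and the destination of the extra tissue do not match. The pass is justified by a shortage for histology. In the split, however, the histology number cannot move and the fat number can. An operator who follows the paragraph literally takes a further needle pass for histology and records the additional sample under a secondary assay.

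The activity score and the fibrosis stage need a readable specimen at both time points, and a subject with one unreadable biopsy contributes no pair. The plan has little room for that. Its power statement assumes 20 pairs, and the five extra places (Study Summary, section 4.4.1) are for withdrawn subjects. An unreadable biopsy is not a listed reason for withdrawal. Section 3.1 already gives up the second biopsy in subjects whose baseline biopsy shows no NASH.

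The written incentives also favour the lipid assay. It has a numeric target, while histology has only visual inspection.

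**Working it through.** **1. The plan's own figure.** Inputs from section 7: paired t-test, two-sided alpha 0.05, effect size d = 0.66, N = 20, power 80%. Power is the probability that a noncentral t with n − 1 degrees of freedom and noncentrality d√n falls outside the two-sided 5% critical values.

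- At n = 20 the noncentrality is 0.66 × √20 = 2.95 and power is 79.9%.
- Solving for 80% power gives n = 20.02 for d = 0.66 (plan: 20), 33.4 for d = 0.5 (plan: 34) and 14.3 for d = 0.8 (plan: 15).

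The sample-size table reproduces.

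**2. Passes against samples.** Assume one sample per pass, so histology samples = passes − fat samples.

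| Passes | Fat | Histology | Listed in the split? |
|---|---|---|---|
| 3 | 1 | 2 | Yes |
| 4 | 2 | 2 | Yes |
| 4 | 1 | 3 | No |

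The listed totals (2+1 = 3 and 2+2 = 4) equal the permitted pass counts, which is why one sample per pass is the natural reading. The only listed split that uses all four cores leaves histology at two. The 3+1 split that would serve the trigger is not listed.

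**3. Can the fourth core still help under 2+2?** Only by substitution: histology would receive the best two of four cores in place of the best two of three. That needs cores to be held uncommitted until the fourth is seen, and section 6.3 wants lipid tissue frozen within minutes of harvest. If one core has been frozen and two are in formalin when the fourth arrives, placing the fourth in formalin gives 3+1. Getting back to 2+2 would mean withdrawing a formalin core for an assay that requires immediate freezing. Substitution is possible but constrained, and it never gives histology a third core.

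**4. What a lost pair costs (illustration only).** Same formula, d = 0.66:

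| Evaluable pairs | Power |
|---|---|
| 20 | 79.9% |
| 19 | 77.7% |
| 18 | 75.2% |

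Each lost pair costs a little over 2 percentage points. This is the price of any lost pair, whatever the cause.

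**5. How many cores does 50 mg need?** Section 6.3 does not say whether its roughly 270 mm is per session. If it is, two lipid samples need 270/2 = 135 mm each and one needs 270 mm. Its figures also do not agree closely. A cylinder of 0.7 mm diameter and 270 mm length holds π × 0.35² × 270 = 103.9 mm³. At an assumed 1 mg per mm³, 50 mg needs only 50/(π × 0.35²) = 130 mm. The text does not say whether 0.7 mm is the needle or the core. The effect of moving one core to histology on the lipid target therefore cannot be calculated from the documents.

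**The case against.** The best defence is that the paragraph does not tie cores to assays by pass order. The cores are inspected by eye, so a good fourth core can go to formalin in place of a poor one and still satisfy 2+2. The stated purpose of the pass also suggests that a sensible operator would do this. In addition, a sample need not equal a pass: with two segments, two samples might mean one container per segment, with the extra pass topping one up.

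Much of this stands. A reader might infer that the histology specimen necessarily stays inadequate after a fourth pass. The documents do not support that, because substitution is open and one sample per pass is an inference. A reader might also infer that the same rule operates at both biopsies, so that the risk arises twice per subject. The month-6 text gives neither trigger nor split, so this is not established either.

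The defence does not remove the mismatch. Substitution and histology priority are nowhere written, the freezing requirement works against substitution, and the one variable number in the split belongs to fat quantification. A sensible operator would have to depart from the listed splits to give histology a third core.

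**Conclusion.** The point holds in a limited form. At baseline the split as written does not serve the only stated reason for the fourth pass. Followed literally, it caps the specimen for the primary endpoint at two samples while a secondary assay gains, so that specimen can stay inadequate unless a better core is swapped in. This rests on reading one sample per pass. At month 6 the gap is different: no trigger and no split are given.

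No size in lost pairs or power can be put on it. A reader might assume, say, 5% inadequate biopsies, compute 1 − 0.95² = 9.75% of pairs lost (about 2 of 20), and conclude that this rule lowers power to 75%. The documents give no such rate. At assumed rates of 2%, 5% and 10% per biopsy, independent between the two biopsies, the same formula gives 0.8, 2.0 and 3.8 pairs of 20. Even these are upper bounds. Only biopsies that fail with the two cores sent but would pass with a third could be charged to the split, and that fraction is unknown. The sample size of 20 is correct and is not in question.

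The correction is still worth making: it is cheap, and it concerns the one specimen on which the primary endpoint depends.

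**What to change.** In sections 3.1, 5.4 and 6, amend the allocation sentence to say that:

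- histology is filled first;
- a pass taken because histology tissue is short goes to formalin, giving up to three samples to histology and one to fat quantification;
- the same allocation rule applies at month 6.

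State whether one sample means one pass. Reconcile the result with the 50 mg target in section 6.3, saying whether that target is per session and what is done when it is not met.

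The cost is a sentence or two in three repeated paragraphs plus a clarification in section 6.3. No pass is added. The real downside is less lipid tissue in the affected subjects. Some may miss the 50 mg target, which would weaken the secondary lipid endpoints and the comparison of spectroscopy with lipidomics in those subjects.
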